5.5.3 Other Efficacy Analysis

Other efficacy variables include:

- pGAI, iGAI, and Swelling Assessment at each scheduled visit,
- percent of subjects with treatment success (upper lips, lower lips) at Visit 3/Month 2 where responder is defined as a subject with at least a 1-grade increase from baseline on the LFGS post augmentation,
- percent of responders (upper lips, lower lips) on the POL severity scale at Visit 4/Month 3 (defined as a subject demonstrating ≥ 1 -point improvement, i.e., decrease in severity, from baseline),
- Subject Satisfaction with Lips VAS at each scheduled visit,
- change from baseline to Visit 4/Month 3 and Visit 5/Month 6 in upper lips, lower lips LFGS.

These other efficacy variables will be summarized for each treatment using descriptive statistics based on the observed data.

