Safety will be assessed by monitoring adverse events (AEs) at all study visits. Adverse Events of Special Interest, any changes in vision and any events attributable to an embolic or ischemic cause (i.e., skin infarction) will be monitored. Other Safety evaluations include lip function, lip sensation, lip texture, lip firmness, lip symmetry, and lip movement/function. Other evaluations include Investigator Ease of Use Assessment, Swelling Assessment, and Subject Satisfaction with Lips Assessment.

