3.2 Sample Size Determination

For the PRO 2018-02 study, the primary variable is change from baseline to Month 3 in LFGS. The sample size was determined based on: (1) both PN40082 and Restylane Silk having an equal mean value with a common standard deviation of 0.85 for change from baseline in LFGS, and (2) the non-inferiority limit of -0.50. The test:control ratio of 1:1 results in 126 (63:63) per-protocol (PP) subjects at power of 90%. A total of 158 subjects will be randomized to obtain 126 (63:63) PP subjects assuming that 80% of randomized subjects meet the PP criteria.

4 Populations To Be Analyzed

Three subject populations are defined as follows:

- (1) As-treated (AT) (safety population): All randomized subjects who received study device. AT subjects will be included in the safety analysis for the treatment they actually received.
- (2) Modified intent-to-treat (mITT): All randomized subjects who met the inclusion/exclusion criteria, and received study device.
- (3) Per-protocol (PP): All randomized subjects who met all inclusion/exclusion criteria; received study device; completed Visit 5/Month 6 within the specified window; had overall LFGS score by the Blinded Evaluating Investigator at Visit 3/Month 2 within the specified visit window; and had no significant protocol violations that would affect the treatment evaluation.

For the purpose of determining the PP status of the subject, "significant protocol violations" are any unforeseen events that occurred during the conduct of the trial that result in noteworthy study protocol violations that could have possibly interfered with the therapeutic administration of the treatment or the precise evaluation of treatment efficacy.

Efficacy analyses will be performed on the mITT and PP populations, with PP as the primary population and mITT supportive. Analyses of safety and other evaluations will be performed on the AT population.

5 Planned Analyses

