5.5 Efficacy Variables

Key efficacy assessments include the following:

- LFGS: 0 = very thin, 1 = thin, 2 = moderately thick, 3 = thick, 4 = full
- POL: 0 = None (a mouth with no perioral lines), 1 = Mild (a mouth with a few shallow perioral lines), 2 = Moderate (a mouth with some moderate lines), 3 = Severe (a mouth with many deep lines or crevices)
- Subject Satisfaction with Lips using a visual analog scale (VAS) on a 100-mm scale from 0 = Very Unsatisfied to 100 = Very Satisfied
- Patient Global Aesthetic Improvement (pGAI) Score: 1=Worse, 2=No change, 3=Improved, 4=Much improved, 5=Very much improved
- Investigator Global Aesthetic Improvement (iGAI) Score: 1=Worse, 2=No change, 3=Improved, 4=Much improved, 5=Very much improved
- Swelling Assessment: 0 = None, 1 = Minimal, 2 = Mild, 3 = Moderate, 4 = Severe

All efficacy analyses will be performed for both the PP and mITT populations.

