5.6 Safety Variables

Key safety variables include incidence rate of treatment-emergent adverse events (TEAEs) and the exposure to the study product, as well as Investigator Ease of Use Assessment, lip function,

lip sensation, lip texture, lip firmness, lip symmetry, and lip movement/function. They will be summarized using the AT population.

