O:\Studies\Prolenium\SYM 2018-02\Biometrics\Programs\Tables\vxix.sas ran on Month Day, Year at hh:mm on data from Month, Day, Year.

Note:

Table 14.2.3.1 will be used as the shell for the following table:

Table 14.2.3.2 – Other Efficacy: Investigator Global Aesthetic Improvement (iGAI) by Visit Based on Observed Data

Table 14.2.3.3 – Other Efficacy: Swelling Assessment by Visit Based on Observed Data

Study Visit	Category	Modified Intent-to-Treat		Per-Protocol	
		PN40082	Restylane Silk	PN40082	Restylane Silk
Visit 2/Month 1	N	0	0	0	0
	0 = None	0 (0%)	0 (0%)	0 (0%)	0 (0%)
	1 = Minimal	0 (0%)	0 (0%)	0 (0%)	0 (0%)
	2 = Mild	0 (0%)	0 (0%)	0 (0%)	0 (0%)
	3 = Moderate	0 (0%)	0 (0%)	0 (0%)	0 (0%)
	4 = Severe	0 (0%)	0 (0%)	0 (0%)	0 (0%)
Visit 3/Month 2					
...					
Visit 5/Month 6	N	0	0	0	0
	0 = None	0 (0%)	0 (0%)	0 (0%)	0 (0%)
	1 = Minimal	0 (0%)	0 (0%)	0 (0%)	0 (0%)
	2 = Mild	0 (0%)	0 (0%)	0 (0%)	0 (0%)
	3 = Moderate	0 (0%)	0 (0%)	0 (0%)	0 (0%)
	4 = Severe	0 (0%)	0 (0%)	0 (0%)	0 (0%)

Source: Listing 16.2.6.1.3

O:\Studies\Prolenium\SYM 2018-02\Biometrics\Programs\Tables\cxxx.sas ran on Month Day, Year at hh:mm on data from Month, Day, Year.

Table 14.2.3.4 – Other Efficacy: Percent of Subjects with Treatment Success on Lip Fullness Grading Scale (LFGS) at Visit 3/Month 2 for Upper Lips and Lower Lips Based on Observed Data

Population	Category	Upper Lips		Lower Lips	
		PN40082	Restylane Silk	PN40082	Restylane Silk
Per-Protocol	N	0	0	0	0
	n (%) of Treatment Success	0 (0.0%)	0 (0.0%)	0 (0.0%)	0 (0.0%)
Modified Intent-to-Treat	N	0	0	0	0
	n (%) of Treatment Success	0 (0.0%)	0 (0.0%)	0 (0.0%)	0 (0.0%)

Treatment success is defined as an achievement of at least a 1-grade increase from baseline on the overall LFGS, where LFGS: 0=Very Thin Lips, 1=Thin Lips, 2=Moderately Thick Lips, 3=Thick Lips, 4=Full Lips.

Source: Listing 16.2.6.2.2, 16.2.6.2.3

O:\Studies\Prolenium\SYM 2018-02\Biometrics\Programs\Tables\xxx.sas ran on Month Day, Year at hh:mm on data from Month, Day, Year.

Note:

Table 14.2.3.4 will be used as the shell for the following table:

Table 14.2.3.5 – Other Efficacy: Percent of Responders on Perioral Lines at Rest (POL) Severity Scale at Visit 4/Month 3 for Upper Lips and Lower Lips Based on Observed Data

With first footnote changed to the following:

Responder is defined as a subject demonstrating at least 1-point improvement, i.e., decrease in severity, from baseline POL severity, where POL severity: 0=None, 1=Mild, 2=Moderate, 3=Severe.

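### The evaluator-graded Swelling Assessment is summarized only on mITT and PP, with no As-Treated table, so the grades of treated subjects who violated eligibility criteria reach no summary

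*SAP*

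**What the plan says.** **SAP.** Section 5.5 includes the Swelling Assessment in its list of key efficacy assessments and then states: "All efficacy analyses will be performed for both the PP and mITT populations". Section 5.5.3 places it with the other efficacy variables, in the item "pGAI, iGAI, and Swelling Assessment at each scheduled visit", and adds: "These other efficacy variables will be summarized for each treatment using descriptive statistics based on the observed data". The shell, "Table 14.2.3.3 – Other Efficacy: Swelling Assessment by Visit Based on Observed Data", has columns for mITT and PP and rows for Visits 2 to 5.

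Section 5.6 lists the safety variables: adverse events, exposure, ease of use, and lip function, sensation, texture, firmness, symmetry and movement. It says of them: "They will be summarized using the AT population". The swelling scale is not in that list, and no table in the 14.3 series covers it. Section 4 says: "Analyses of safety and other evaluations will be performed on the AT population".

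**Protocol.** The scale is classified in two ways. Section 7.1 says: "Other evaluations include Investigator Ease of Use Assessment, Swelling Assessment, and Subject Satisfaction with Lips Assessment", and the synopsis groups it likewise. But the efficacy part of the synopsis and sections 7.8.3 and 8.2 list it as other efficacy. Section 7.9.2, on other safety evaluations, does not name it.

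**The concern.** The scale in Protocol 7.6.16 grades enlargement beyond the intended augmentation. Grade 3 means that a lip looks abnormally large; grade 4 means that speech, eating or drinking is impaired. Higher is worse, and Protocol 7.9.3.1 names swelling as an expected adverse event. A harm of this kind is normally summarized on everyone treated, by the device received. Here it takes its populations from the efficacy label, and PP is the primary efficacy population.

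The mITT set removes treated subjects who broke an eligibility criterion. Those criteria include hypersensitivity history, anticoagulant use, recent immunosuppressive use and active facial inflammation, so the removed subjects need not have the same swelling risk as the rest. PP also requires Visit 5 within its window, and leaving the study can follow from harm: a subject unblinded so that an adverse event can be managed must be withdrawn (Protocol 7.3.3 and 7.9.10.2). What is at stake is a complete by-arm description of graded swelling. No test is planned on it.

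**Working it through.** **1. The plan's own figures.** Inputs from SAP 3.2: SD 0.85, margin 0.50, true difference 0, power 90%, 1:1 allocation; one-sided 0.025 follows from the 95% interval in Protocol 8.2. With the normal formula, n per arm = 2 × (1.960 + 1.282)² × 0.85² / 0.50² = 60.7, so 61; the t-based version gives 62. The plan states 63, at which power is 0.910 (normal) or 0.906 (t). Then 126 / 0.80 = 157.5, rounded up to 158, as stated. Nothing in this point disputes the sample size; it supplies the denominators.

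**2. Who is missing from which summary.** From the definitions in SAP section 4:

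| Treated subject | AT | mITT | PP |
|---|---|---|---|
| Eligible, completes Visit 5 in window, meets other PP rules | in | in | in |
| Eligible, leaves early or misses the Visit 5 window | in | in, at visits attended | out |
| Violated an eligibility criterion | in | out | out |

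Only the last row is lost from both columns of Table 14.2.3.3.

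**3. How many.**
- PP: 158 − 126 = 32 subjects, 32/158 = 20.3%, or 16 per arm, for any reason.
- mITT: the documents give no violator rate. Assuming all 158 are treated, rates of 0, 2, 5 and 10% give about 0, 3, 8 and 16 subjects.

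**4. What that could do to a rate (illustration).** Take one arm of 79 and assume that 10% of the retained subjects have swelling at or above some grade. The 5% and 10% violator rates, split evenly, exclude 4 and 8 subjects per arm.
- 4 excluded: 75 retained, 7.5 expected cases. The AT rate lies between 7.5/79 = 9.5% (no excluded subject affected) and 11.5/79 = 14.6% (all affected).
- 8 excluded: 71 retained, 7.1 expected cases. The AT rate lies between 7.1/79 = 9.0% and 15.1/79 = 19.1%.

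These are bounds under assumed inputs, not predictions.

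**5. Grades outside the scheduled visits.** Protocol 7.7.7 and 7.7.8 allow swelling to be graded at early termination and at unscheduled visits. Table 14.2.3.3 has rows for scheduled visits only. The SAP 5.2 rule that moves termination-visit data to the nearest scheduled visit is written as preparation for multiple imputation, which covers overall LFGS only. Where these swelling grades would be shown is unclear.

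**The case against.** Four stronger readings are tempting, and the documents do not support them.

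- **Early leavers vanish from the swelling comparison.** They do not. mITT has no completion requirement, and the table uses observed data, so they count at each visit attended, just as in an AT table. A reader might suppose that 5 of 79 subjects are affected at Visit 2 and 3 of these later leave, and contrast 5/79 = 6.3% with a PP rate of 2/63 = 3.2%. If all 79 are eligible, the mITT column beside it still shows 5/79.
- **Swelling is never analysed on AT.** Swelling reported as a treatment-emergent adverse event is tabulated on AT by preferred term, severity and relationship (SAP 5.6.1), and the adverse event listing shell uses injection site swelling as its example. Only the graded scale is missing.
- **SAP section 4 contradicts SAP 5.5.3.** In SAP 3.1 the phrase other evaluations covers only ease of use, which is summarized on AT. The conflict arises only if the grouping in Protocol 7.1 is carried into SAP section 4, and the protocol also lists swelling as other efficacy.
- **The comparison is biased in favour of one device.** The summary is descriptive and the violators' number and arm are unknown, so no direction can be stated. Listing 16.2.6.1.3 carries an AT flag, so the excluded grades may be listed.

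All four corrections stand. They do not make the adverse event tables a substitute for the scale. Specific events are not to be elicited (Protocol 7.9.5), diaries cover two weeks after each treatment (7.6.24), diary events that outlast the diary become adverse events at the investigator's discretion (7.9.8), and severity is graded by effect on daily activity (7.9.6.1). The comparator's instructions for use report delayed reactions at 21 to 142 days, and 26 of its 35 late lip events were swelling. In that period the scale at Visits 2 to 5 is the plan's systematic graded measure.

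**Conclusion.** The point holds in a limited form. A scale whose upper grades describe harm is summarized only on mITT and PP, while the other evaluator-rated lip assessments are summarized on AT. Treated eligibility violators are absent from both swelling summaries: 0 to 16 of 158, if violators are 0 to 10% and everyone randomized is treated. The true number is unknown and probably small. A further group, within the 32 expected outside PP for any reason, is absent from the PP columns only. No planned inference is affected. The change is worth making because it uses data already collected and removes post-randomization exclusions from a harm summary.

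**What to change.** 1. Add an As-Treated version of Table 14.2.3.3, by treatment received, at each scheduled visit, and name it in SAP 5.6.
2. In that table, add a row for the worst post-baseline grade per subject, counting early-termination and unscheduled grades.
3. Keep the mITT and PP columns as they are.
4. Reconcile the protocol's two classifications (other evaluation in the synopsis and 7.1; other efficacy in the synopsis efficacy section, 7.8.3 and 8.2) with SAP section 4, by stating there which population or populations apply to swelling.

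The cost is one extra table shell and a few lines of SAP text. No new data are needed, and the sample size does not change.

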5.6 Safety Variables

Key safety variables include incidence rate of treatment-emergent adverse events (TEAEs) and the exposure to the study product, as well as Investigator Ease of Use Assessment, lip function,

lip sensation, lip texture, lip firmness, lip symmetry, and lip movement/function. They will be summarized using the AT population.

5.6.1 Adverse Events

All adverse events (AEs) occurring during the study will be recorded and coded in the Medical Dictionary for Regulatory Activities (MedDRA), version 20 or higher. TEAEs are defined as events that appear subsequent to the first injection or that were present prior to the first injection but worsened in intensity after the first injection.

Frequency and percent of subjects reporting TEAEs will be tabulated for each treatment by system organ class and preferred terms, and further by severity and relationship to study device. In summaries of severity and relationship, subjects who reported more than one event in a treatment arm that are mapped to the same preferred term will be counted only once in that treatment arm under the strongest severity and relationship, respectively.

TEAEs related to vascular injections/Visual events will also be tabulated by subject Fitzpatrick Skin Type (I-III vs. IV-VI), each Fitzpatrick Skin Type individually and by number of injections subjects received. Most frequently occurring TEAEs related to vascular injections/Visual events (those reported by 5% or more subjects of either treatment group) will be tabulated by preferred term. These TEAEs will also be summarized by event's severity and duration.

Treatment-Emergent Serious Adverse Events (TESAEs) and TEAEs that led to treatment interruption or discontinuation will be presented in data listings.

5.6.2 Exposure to Study Product

Amount of syringe used will be summarized using descriptive statistics (mean, SD, minimum, median, maximum) at Visit 1 for all the AT subjects and at Visit 2/Month 1 for those who received a touch-up treatment.

5.6.3 Other Variables

Investigator Ease of Use Assessment

Overall ease of use of the device will be evaluated by the Treating Investigator using the numerical rating scale (NRS) from 0 being not easy to 10 being most easy at Visit 1/Day 1 and for subjects who have touch-up treatment at Visit 2/Month 1. It will be summarized for the AT subjects descriptively with mean, SD, minimum, median, and maximum.

Lip Evaluations

Lip function, lip sensation, lip texture, lip firmness, lip symmetry, and lip movement/function will be evaluated by the Blinded Evaluating Investigator at each visit. These variables will be summarized using frequency and percent of subjects by categories of incidence.

Concomitant Medications

Concomitant medications will be coded using the World Health Organization (WHO) Drug Dictionary, Version March 2013 or later, and will be presented in data listings.

5.7 Other Analysis

Blinding of subjects and evaluators will be assessed at Visit 5/Month 6, end of study or early termination. Both subjects and blinded evaluating investigators will be asked to identify which treatment they thought had been administered. The results of subject guesses and results of blinded evaluator guesses will be compared to the actual treatment assignment separately. The null hypothesis to be tested is that the proportion of correct guesses is 50%, using p-values and 95% confidence intervals from the exact binomial distribution. A correct guess is defined as guessing PN40082 when the subject was randomized to PN40082 or guessing Restylane Silk when the subject was randomized to Restylane Silk. The proportion of correct guesses is defined to be the number of subjects who guessed correctly divided by the number of subjects who responded.

6 Tables and Listings

The following is an example of tables and listings that will be included in the clinical study report. Tables and listings may be modified as needed during the data analyses.

7 Appendices

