#### **7.4.4 Blinding of Study Device**

Injections of the study device are performed by the unblinded Treating Investigator. The blinded Evaluating Investigator is not allowed to retrieve study supplies or to be present during opening of the study supplies or during the injections. The Treating Investigator is not to have any discussion with the Evaluating Investigator or subjects regarding the treatments.

Subjects are blinded to treatment assignment. Subjects are physically masked (blindfolded) just prior to and during all injection procedures to prevent observation of the syringes containing study device.

Subjects, investigators, the Sponsor's staff conducting the study, and members of the administrative team will not have access to individual subjects' treatment assignments. In the event of an emergency that requires breaking of the study blind, the randomization code will be maintained by each investigator that can be opened to reveal the study device.

See Section 7.9.10.2 for a description of the method of unblinding a subject during the study if such action is warranted.

At Visit 5, subjects and blinded evaluating investigators will be asked which treatment they thought was administered as a way of evaluating the blinding.

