	n (%) subjects able to sip liquid through a straw	0 (0%)	0 (0%)
Visit 5/Month 6	N	0	0
	n (%) subjects able to sip liquid through a straw	0 (0%)	0 (0%)

Source: Listing 16.2.4.8

O:\Studies\Prollenium\SYM 2018-02\Biometrics\Programs\Tables\ccx.sas ran on Month Day, Year at hh:mm on data from Month, Day, Year.

Note:

Table 14.3.4.1 will be used as the shell for the following table:

Table 14.3.4.2 – Lip Sensation Test (Cotton Wisp) by Visit for As-Treated Population

Table 14.3.4.3 – Lip Sensation Test (0.4G Monofilament) by Visit for As-Treated Population

Table 14.3.4.4 – Lip Texture Evaluation by Visit for As-Treated Population

Study Visit	Category	PN40082	Restylane Silk
Visit 1/Day 1 (Prior to injection)	N	0	0
	n (%) Normal	0 (0%)	0 (0%)
	n (%) Abnormal	0 (0%)	0 (0%)
	- n (%) Abnormal: Mild	0 (0%)	0 (0%)
	- n (%) Abnormal: Moderate	0 (0%)	0 (0%)
	- n (%) Abnormal: Severe	0 (0%)	0 (0%)
Visit 2/Month 1 (Prior to touch-up)	...		
	...		
Visit 3/Month 2			
Visit 4/Month 3			
Visit 5/Month 6			

Source: Listing 16.2.4.9

O:\Studies\Prollenium\SYM 2018-02\Biometrics\Programs\Tables\ccx.sas ran on Month Day, Year at hh:mm on data from Month, Day, Year.

Note:

Table 14.3.4.4 will be used as the shell for the following table:

Table 14.3.4.5 – Lip Firmness Evaluation by Visit for As-Treated Population

Table 14.3.4.6 – Lip Symmetry Evaluation by Visit for As-Treated Population

Table 14.3.4.7 – Lip Movement/Function Evaluation by Visit for As-Treated Population

Study Visit	Category	PN40082	Restylane Silk
Visit 1/Day 1 (Prior to injection)	N	0	0
	n (%) Normal – Subject’s ability to pucker lips	0 (0%)	0 (0%)
	n (%) Normal – Subject’s ability to blow with lips	0 (0%)	0 (0%)
	n (%) Normal – Subject’s ability to pronounce words that begin with “W”	0 (0%)	0 (0%)
Visit 2/Month 1 (Prior to touch-up)	...		
	...		
Visit 3/Month 2			
Visit 4/Month 3			
Visit 5/Month 6			

Source: Listing 16.2.4.8

O:\Studies\Prolenium\SYM 2018-02\Biometrics\Programs\Tables\ccx.sas ran on Month Day, Year at hh:mm on data from Month, Day, Year.

Table 14.3.5 – Other Analysis: Assessment of Blinding to Subjects and Evaluators at End of Study

Assessed by Subject or Evaluator	Treatment Subject Received	Treatment Guessed	n/N ¹ (%)	P-value and 90% Confidence Interval ²
By Subject	PN40082	PN40082	0/0 (0%)	(0.0%, 0.0%)
		Restylane Silk	0/0 (0%)	
		Unsure	0/0 (0%)	
	Restylane Silk	PN40082	0/0 (0%)	
		Restylane Silk	0/0 (0%)	
		Unsure	0/0 (0%)	
Overall Correct Guesses		0/0 (0%)		

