By Evaluator	PN40082	PN40082	0/0 (0%)	(0.0%, 0.0%)
		Restylane Silk	0/0 (0%)	
		Unsure	0/0 (0%)	
	Restylane Silk	PN40082	0/0 (0%)	
		Restylane Silk	0/0 (0%)	
		Unsure	0/0 (0%)	
Overall Correct Guesses		0/0 (0%)		

¹ N = Total number of responses, n = number of responses associated with a given combination (e.g. number of subjects who received PN40082 and guessed Restylane Silk).

² P-values and 95% confidence intervals from the exact binomial distribution to test the null hypothesis that the proportion of correct guesses is 50%.

Source: Listing 16.2.1.2

O:\Studies\Prolenium\SYM 2018-02\Biometrics\Programs\Tables\ccx.sas ran on Month Day, Year at hh:mm on data from Month, Day, Year.

Subject Listings

Listing 16.2.1.1 – Subject Analysis Status

Site-Subject Treatment:	As-Treated (AT)		Modified Intent-to-Treat (mITT)		Per-Protocol (PP)	
	Included?	Reason for Not Included	Included?	Reason for Not Included	Included?	Reason for Not Included

O:\Studies\ Prolenium\SYM 2018-02\Biometrics\Programs\Listing\xxx.sas ran on Month Day Year at hh mm on data from Month Day, Year.

Listing 16.2.1.2 – Subject Disposition and Assessment of Blinding at End of Study

Site- Subject	Analy	Subject Disposition	Date Completed or Discontinued	Reason, if discontinued	Evaluation of Subject for Participation in PRO 2018-03 study			Subject was asked to identify treatment he received? If Yes, response	Blinded evaluating investigator was asked to identify treatment subject received? If Yes, response
					Subject underwent consent?	Subject agreed to participate?	Evaluator		
Treatment:									

Analys (Analyses): A = As-Treated (AT) Analyses, M = Modified Intent-to-Treat (MITT) Analyses, P = Per-Protocol Analyses

O:\Studies\ Prolenium\SYM 2018-02\Biometrics\Programs\Listing\xxx.sas ran on Month Day Year at hh mm on data from Month Day, Year.

Listing 16.2.1.3 – Dates of Visits

Site- Subject	Analyses	Visit 1/ Day 1 (Baseline)	Visit 2/ Month 1 Day 28 (± 2 days) [Day #]	Visit 3/ Month 2 Day 56 (± 4 days) [Day #]	Visit 4/ Month 3 Day 84 (± 4 days) [Day #]	Visit 5/ Month 6 Day 168 (± 7 days) [Day #]	No. of UVs: Unscheduled Visit(s) [Day #]
Treatment:							

Analyses: A = As-Treated (AT) Analyses, M = Modified Intent-to-Treat (MITT) Analyses, P = Per-Protocol Analyses

Day # (Study Days) = Visit Date - Baseline (Visit 1) Date +1.

O:\Studies\ Prollenium\SYM 2018-02\Biometrics\Programs\Listing\xxx.sas ran on Month Day Year at hh mm on data from Month Day, Year.

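### The blinding test counts 'Unsure' answers in its denominator but still tests for 50% correct, so moderate unblinding can be masked

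*SAP*

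**What the plan says.** Protocol 7.4.4 has subjects and blinded evaluating investigators "asked which treatment they thought was administered as a way of evaluating the blinding" at Visit 5; Protocol 7.6.26 adds early termination.

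SAP 5.7 sets the test: "The null hypothesis to be tested is that the proportion of correct guesses is 50" per cent, by the exact binomial distribution with a 95% CI, for subjects and evaluators separately. The denominator is everyone who answered: "The proportion of correct guesses is defined to be the number of subjects who guessed correctly divided by the number of subjects who responded". Section 5.7 says nothing about 'Unsure'.

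The shell of Table 14.3.5 offers three answers in each arm: PN40082, Restylane Silk and 'Unsure'. Footnote 1 gives "N = Total number of responses". Footnote 2 repeats the test: "P-values and 95% confidence intervals from the exact binomial distribution to test the null hypothesis that the proportion of correct guesses is 50" per cent.

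Two details disagree:

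- **CI level.** The table's column header reads "P-value and 90% Confidence Interval", against 95% in 5.7 and in footnote 2.
- **Correct guess.** Section 5.7 goes by randomized arm ("A correct guess is defined as guessing PN40082 when the subject was randomized to PN40082"), while the table's rows are headed "Treatment Subject Received".

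**The concern.** A guess is correct only if it names a product that matches the arm. An 'Unsure' answer therefore adds to the denominator and never to the numerator, yet the null stays at 50%. That null is right only if nobody answers 'Unsure'.

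Two errors follow:

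- **Masking.** If those who name a product are right more often than chance, the 'Unsure' answers pull the tested proportion back towards 50%, and real unblinding can look like chance.
- **Miscalibration.** If the blind is intact, the proportion falls below 50% and the two-sided test may reject. That result shows a wrong null, not a broken blind.

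This is the only planned test of the blind. The injector is unblinded, and the primary endpoint is a graded rating that depends on the evaluator staying blinded.

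**Working it through.** **Inputs from the documents.** Null 50%, exact binomial (SAP 5.7); two-sided, p below 0.05 (SAP 5.1); 1:1 allocation (SAP 3.1); 158 randomized and 126 expected per-protocol (SAP 3.2).

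**Assumptions, because the documents give no values.** u is the share answering 'Unsure' (5% to 30%). q is the share correct among those who name a product (50% is a perfect blind; 60%, 70% and 80% are increasing unblinding). The number of responses is n = 150, with 126 and 158 as checks. Responses are independent.

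**Step 1: the chance value.** The SAP gives no derivation of its 50%. With 1:1 allocation, someone who names a product under a perfect blind is right half the time, whichever product is favoured. So

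expected correct ÷ all responses = (1−u) × 0.5 = 0.5 − u/2.

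This is 50% at u = 0, 45% at 10%, 40% at 20% and 35% at 30%. The null is too high by u/2.

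**Step 2: where unblinding disappears.** In general the tested proportion has expectation (1−u)q. It equals exactly 50% when u = 1 − 0.5/q:

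- q = 60%: 1 − 0.5/0.6 = 17% unsure
- q = 70%: 1 − 0.5/0.7 = 29% unsure
- q = 80%: 1 − 0.5/0.8 = 38% unsure

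**Step 3: detection.** At n = 150 the exact two-sided 5% test rejects at 62 or fewer, or 88 or more, correct. To reach 88, accuracy among those who name a product must be at least 88/[150(1−u)]: 59%, 65%, 73% and 84% at u = 0, 10%, 20% and 30%.

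The table gives the probability of rejecting in the direction of unblinding, P(X ≥ 88) with X ~ Bin(150, (1−u)q). In brackets is the same probability when only named guesses are tested, with the number named ~ Bin(150, 1−u).

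| q | u = 5% | u = 10% | u = 20% | u = 30% |
|---|---|---|---|---|
| 60% | 37% (64%) | 14% (62%) | 0.6% (56%) | – |
| 70% | 98% (99.8%) | 88% (99.7%) | 28% (99.3%) | 1.1% (98.5%) |
| 80% | – | – | 92% (>99%) | 28% (>99%) |

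At q = 70%, u = 30% the planned test rejects 4.7% of the time in total, but most of that is in the wrong direction. At q = 70%, u = 20%, detection is 24% with n = 126 and 32% with n = 158.

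**Step 4: a perfect blind (q = 50%), n = 150.**

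| u | rejects, too few correct | rejects, too many correct |
|---|---|---|
| 0 | 2.0% | 2.0% |
| 5% | 7.6% | 0.4% |
| 10% | 20.6% | 0.05% |
| 20% | 66.3% | about 0 |
| 30% | 95.5% | about 0 |

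Total rejection passes 50% at u of about 18% (n = 126), 17% (n = 150) and 16% (n = 158). Testing named guesses only keeps total rejection near 4%.

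**Step 5: one possible table (q = 70%, u = 20%).** Of 150 responses, 30 are 'Unsure' and 84 of the 120 named guesses are correct.

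- As planned: 84/150 = 56.0%, 95% CI 47.7 to 64.1, p = 0.16.
- Named guesses only: 84/120 = 70.0%, 95% CI 61.0 to 78.0, p = 0.00001.

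These figures suit the subject guesses. Evaluator guesses come from few raters at about seven sites and are clustered, so neither calculation is exact for them.

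**The case against.** - **The reading is inferred.** Section 5.7 never mentions 'Unsure', so 'responded' could mean 'named a product'. The option appears only in a shell, and SAP section 6 says tables may be modified. This does not remove the problem: the shell and its footnote count 'Unsure' as a response, and the denominator and the 50% null both stand in the body of 5.7. If the narrower meaning was intended, the text must say so.
- **The size depends on unknowns.** This stands. With few 'Unsure' answers or very strong unblinding, little is lost: detection is 98% at u = 5%, q = 70%, and 92% at u = 20%, q = 80%.
- **The figures fit subjects, while the primary endpoint is rated by evaluators.** This also stands. The u/2 offset applies to evaluators too, but the rejection rates assume independence, and excluding 'Unsure' does not cure clustering.
- **The table allows recalculation.** It prints the counts by arm, so a careful reader could rework the result. The planned proportion, p-value and CI would still be the wrong ones.
- **'Unsure' is itself evidence that the blind held, and dropping it leaves a self-selected group.** This is fair. It is a reason to report the 'Unsure' share by arm, or to use a blinding index, but not to keep a 50% null on a denominator that includes it.

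**Conclusion.** The concern holds. Read with its own table, SAP 5.7 tests a null that is too high by half the 'Unsure' share, and nothing in either document excludes those answers or adjusts for them. The offset needs no assumption beyond 1:1 allocation and at least one 'Unsure' answer.

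The practical size does rest on assumed u, q, n and independence. The main consequence is loss of detection: at about 20% unsure, unblinding at 60% to 70% accuracy would usually be missed. Rejections under a perfect blind fall almost entirely on the low side and would not look like unblinding.

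This is an 'Other Analysis' with no part in the non-inferiority decision. It should be corrected because it is the only planned test of the blind. The CI-level and correct-guess discrepancies are minor; the second matters only for a subject who received the product they were not randomized to.

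**What to change.** 1. Add one sentence to SAP 5.7: the proportion correct, its exact p-value and its 95% CI are computed among respondents who named a product, with 'Unsure' excluded from the test and its counts shown by arm, for subjects and evaluators separately. A blinding index by arm that handles 'Unsure' is an acceptable alternative.
2. Match the overall-correct line of Table 14.3.5 and its N to that sentence.
3. Change the column header from 90% to 95%.
4. Use one definition of a correct guess, by randomized arm or by treatment received, in both places.
5. When reporting evaluator results, note that the exact binomial ignores clustering by rater.

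The cost is a sentence in 5.7 and small edits to one table shell. No new data are needed.
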